2.5.2.2 Statistical hypothesis, model, and method of analysis

Statistical hypothesis and testing strategy

The following null hypotheses (H_0) will be tested against the respective alternative hypotheses (H_A) in a closed testing procedure ([Bretz et al 2009](#)), thus controlling the family-wise type I error which is set to 0.025 (one-sided):

Primary:

UAS7 score change from baseline at Week 12

H_{01} : $\mu_{\text{remibrutinib}} \geq \mu_{\text{Placebo}}$ versus H_{A1} : $\mu_{\text{remibrutinib}} < \mu_{\text{Placebo}}$

where μ is the mean change from baseline in UAS7 at Week 12

Secondaries:

- **UAS7 \leq 6 at Week 12**

H_{02} : $p_{\text{remibrutinib}} \leq p_{\text{Placebo}}$ versus H_{A2} : $p_{\text{remibrutinib}} > p_{\text{Placebo}}$

where p is the proportion of participants achieving UAS7 \leq 6 at Week 12,

- **UAS7 = 0 at Week 12**

H_{03} : $p_{\text{remibrutinib}} \leq p_{\text{Placebo}}$ versus H_{A3} : $p_{\text{remibrutinib}} > p_{\text{Placebo}}$

where p is the proportion of participants achieving UAS7=0 at Week 12,

- **ISS7 score change from baseline at Week 12**

H_{04} : $\mu_{\text{remibrutinib}} \geq \mu_{\text{Placebo}}$ versus H_{A4} : $\mu_{\text{remibrutinib}} < \mu_{\text{Placebo}}$

where μ is the mean change from baseline in ISS7 at Week 12,

- **HSS7 score change from baseline at Week 12**

$H_{05}: \mu_{\text{remibrutinib}} \geq \mu_{\text{Placebo}}$ Versus $H_{A5}: \mu_{\text{remibrutinib}} < \mu_{\text{Placebo}}$

where μ is the mean change from baseline in HSS7 at Week 12,

- **UAS7 ≤ 6 at Week 2**

$H_{06}: p_{\text{remibrutinib}} \leq p_{\text{Placebo}}$ versus $H_{A6}: p_{\text{remibrutinib}} > p_{\text{Placebo}}$

where p is the proportion of participants achieving UAS7 ≤ 6 at Week 2,

- **DLQI = 0/1 at Week 12**

$H_{07}: p_{\text{remibrutinib}} \leq p_{\text{Placebo}}$ versus $H_{A7}: p_{\text{remibrutinib}} > p_{\text{Placebo}}$

where p is the proportion of participants achieving DLQI = 0/1 at Week 12,

- **Cumulative number of weeks with an UAS7 ≤ 6 response between baseline and Week 12**

$H_{08}: \mu_{\text{remibrutinib}} \leq \mu_{\text{Placebo}}$ versus $H_{A8}: \mu_{\text{remibrutinib}} > \mu_{\text{Placebo}}$

where μ is the mean cumulative number of weeks that participants achieve UAS7 ≤ 6 response between baseline and Week 12,

[figure not shown]
- **Cumulative number of weeks with an AAS7=0 response between baseline and Week 12**

$H_{09}: \mu_{\text{remibrutinib}} \leq \mu_{\text{Placebo}}$ versus $H_{A9}: \mu_{\text{remibrutinib}} > \mu_{\text{Placebo}}$

where μ is the mean cumulative number of weeks that participants achieve AAS7=0 response between baseline and Week 12,

A graphical representation of the testing strategy is presented in [Figure 2-1](#)

Figure 2-1 Testing strategy with UAS7 as the primary endpoint

The value inside the circle represents the significance level. The arrow and value inside the square represent the "alpha-propagation".

The first hypothesis is tested with full level alpha (0.025 one-sided). If significant, the second hypothesis is tested with full-level alpha; otherwise, the testing procedure stops. The testing is strictly hierarchical, so that null hypotheses can be tested along the pre-defined order at the level assigned until a null hypothesis cannot be rejected, at which point the testing stops. Furthermore, the testing strategy reflects the separation of primary and secondary endpoints, so that hypotheses related to secondary endpoints will only be tested if the null hypothesis related to the primary endpoint is rejected.

Statistical model and method of analysis

1. UAS7 \leq 6 at Week 12

The proportion of participants with $UAS7 \leq 6$ at Week 12 will be analyzed using a logistic regression model including treatment group, region, prior exposure to anti-IgE biologics and baseline UAS7 score as covariate.

2. UAS7 = 0 at Week 12

The proportion of participants with $UAS7 = 0$ at Week 12 will be analyzed using a logistic regression model including treatment group, region, prior exposure to anti-IgE biologics and baseline UAS7 score as covariate.

3. ISS7 score change from baseline at Week 12

The absolute change from baseline in ISS7 score at Week 12 will be analyzed using MMRM modeling including treatment group, baseline ISS7 score, randomization strata variables, week and both interaction of treatment by week and interaction of baseline ISS7 score by week as fixed effects.

4. HSS7 score change from baseline at Week 12

The absolute change from baseline in HSS7 score at Week 12 will be analyzed using MMRM modeling including treatment group, baseline HSS7 score, randomization strata variables, week and both interaction of treatment by week and interaction of baseline HSS7 score by week as fixed effects.

5. UAS7 \leq 6 at Week 2

The proportion of participants with $UAS7 \leq 6$ at Week 2 will be analyzed using a logistic regression model including treatment group, region, prior exposure to anti-IgE biologics and baseline UAS7 score as covariate.

6. DLQI = 0/1 at Week 12

The proportion of participants with overall DLQI scores ≤ 1 at Week 12 will be analyzed using a logistic regression model which includes treatment group, region, prior exposure to anti-IgE biologics and baseline DLQI score.

7. Cumulative number of weeks with an $UAS7 \leq 6$ response between baseline and Week 12

The cumulative number of weeks achieving $UAS7 \leq 6$ response between baseline and Week 12 will be modelled using a negative binomial regression model with log link, using treatment group, region, and prior exposure to anti-IgE biologics. The patient's time in the treatment period up to Week 12 (natural log of proportion of time in treatment period, i.e., natural log of [number of weeks with the response variable in treatment period/12 weeks]) is used as an offset variable to obtain the $UAS7 \leq 6$ rate, adjusted for the varying lengths of patient's time in the randomized treatment period.

8. Cumulative number of weeks with an $AAS7 = 0$ response between baseline and Week 12

The cumulative number of weeks achieving $AAS7 = 0$ response between baseline and Week 12 will be modelled using a negative binomial regression model with log link, using treatment

group, region, prior exposure to anti-IgE biologics and baseline AAS7 = 0 status. The patient's time in the treatment period up to Week 12 (natural log of proportion of time in treatment period, i.e., natural log of [number of weeks with the response variable in treatment period/12 weeks]) is used as an offset variable to obtain the AAS7=0 rate, adjusted for the varying lengths of patient's time in the randomized treatment period.

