Amendment 1 implements recommendations from the US FDA regarding statistical analysis for covering intercurrent event handling for COVID-19 related reasons for treatment discontinuation and the use of the same covariates in both primary and secondary endpoints. In addition, feedback received from Health Authorities and Institutional Review Boards (IRBs)/Independent Ethics Committees (IECs) for both pivotal Phase 3 trials (CLOU064A2301 and CLOU064A2302) was considered to ensure consistency across the program and the protocol amended as indicated below.

[figure not shown]
Furthermore, clarifications and corrections were made, and [Section 4.5](#) Risks and benefits has been amended to include updates from the LOU064 Investigator Brochure Edition 9 (03-May-2022) as indicated below.

At the time of this amendment (V01) release, enrollment is ongoing with 226 patients screened and 123 patients randomized.

Changes to the protocol

[figure not shown]
Changes to specific sections of the protocol are shown in the track changes version of the protocol using strike through red font for deletions and red underline for insertions.

- [REDACTED]
- [Section 2.2](#): Methods for handling of intercurrent events have been updated considering US FDA feedback.
- [Section 4.5](#): Risks and benefits has been amended to include updates from the LOU064 Investigator Brochure Edition 9. No change to risk-benefit assessment of the study.
- [Section 5.2](#): Exclusion criteria 13 and 18 updated to reflect the feedback received from Health Authorities, exclusion criteria 19 updated to clarify maximum dose of clopidogrel.
- [Section 6.2.3](#): Clarification that immunomodulating biologics are considered prohibited medication under immunosuppressive medications; prohibition period for live attenuated vaccines updated to reflect feedback from Health Authorities; maximum dose for long-term clopidogrel use added. Clarification that live attenuated vaccines are prohibited 6 weeks prior to randomization and at least until 4 weeks after last dose of study treatment as consistent with exclusion criteria and Investigator Brochure. Remibrutinib updated with study treatment for clarification.
- [Section 6.6](#): Clarification that interruptions are permitted related to study treatment

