5.1 Inclusion criteria

Participants eligible for inclusion in this study must meet **all** of the following criteria:

1. Signed informed consent must be obtained prior to participation in the study
2. Male and female adult participants ≥ 18 years of age at the time of screening
3. CSU duration for ≥ 6 months prior to screening (defined as the onset of CSU determined by the investigator based on all available supporting documentation)

4. Diagnosis of CSU inadequately controlled by second generation H1-antihistamines at the time of randomization defined as:
 - The presence of itch and hives for ≥ 6 consecutive weeks prior to screening despite the use of second generation H1-antihistamines during this time period
 - UAS7 score (range 0-42) ≥ 16 , ISS7 score (range 0-21) ≥ 6 and HSS7 score (range 0-21) ≥ 6 during the 7 days prior to randomization (Day 1)
5. Documentation of hives within three months before randomization (either at screening and/or at randomization; or documented in the participants' medical history)
6. Willing and able to complete an Urticaria Patient Daily Diary (UPDD) for the duration of the study and adhere to the study protocol
7. Participants must not have had more than one missing UPDD entry (either morning or evening) in the 7 days prior to randomization (Day 1)

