- No impact on participants' dermatology quality of life at Week 12, assessed as proportion of participants achieving DLQI = 0-1.

An overall score will be calculated according to the scoring manual. The proportion of participants with overall DLQI scores ≤ 1 at Week 12 will be analyzed using a logistic regression model which includes treatment group, region, prior exposure to anti-IgE biologics and baseline DLQI score.

- Cumulative number of weeks that participants achieve $UAS7 \leq 6$ responses between baseline and Week 12.

The cumulative number of weeks achieving $UAS7 \leq 6$ response between baseline and Week 12 will be derived based on the eDiary. The cumulative number of weeks achieving $UAS7 \leq 6$ response between baseline and Week 12 will be modelled using a negative binomial regression model with log link, using treatment group, region, and prior exposure to anti-IgE biologics. The number of weeks stay on the trial will be used as an offset.

- Cumulative number of weeks that participants achieve $AAS7 = 0$ responses between baseline and Week 12.

The cumulative number of weeks achieving $AAS7 = 0$ response between baseline and Week 12 will be derived based on the AAS eDiary and UPDD diary. A weekly AAS7 score will be derived by adding up the daily scores of the 7 days preceding the visit, and ranges from 0 to 105. If the AAS7 assessment is missing, it will be considered as a non-response for the cumulative number of weeks that participants achieve $AAS7 = 0$ response calculation.

The cumulative number of weeks achieving $AAS7 = 0$ response between baseline and Week 12 will be modelled using a negative binomial regression model with log link, using treatment group, region, prior exposure to anti-IgE biologics and baseline $AAS7 = 0$ status.

Statistical model, hypothesis, and method of analysis for scenario with UAS7 as the primary efficacy endpoint

Testing strategy

The following null hypotheses (H_0) will be tested against the respective alternative hypotheses (H_A) in a closed testing procedure (Bretz et al 2009), thus controlling the family-wise type I error which is set to 0.025 (one-sided):

Primary:

UAS7 score change from baseline at Week 12

$$H_{01}: \mu_{\text{remibrutinib}} \geq \mu_{\text{Placebo}} \text{ versus } H_{A1}: \mu_{\text{remibrutinib}} < \mu_{\text{Placebo}}$$

where μ is the mean change from baseline in UAS7 at Week 12,

Secondaries:

- **UAS7 ≤ 6 at Week 12**

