5.4.2.3 Negative binomial regression

Count variable including the cumulative number of weeks achieving AAS7= 0 response between baseline and Week 12 or the cumulative number of weeks achieving UAS7≤6 response will be modelled using a negative binomial regression model with log link, using treatment group, randomization strata factors (i.e. geographic region and prior exposure to anti-IgE biologics, and baseline AAS7=0 status (for AAS7 = 0 response only). The patient's time in the treatment period up to Week 12 (natural log of proportion of time in treatment period, i.e., natural log of [number of weeks with the response variable in treatment period/12 weeks]) is used as an offset variable. The patient's time in the treatment period up to Week 24 (natural log of proportion of time in treatment period, i.e., natural log of [number of weeks with the response variable in treatment period/24 weeks]) is used as an offset variable.

If the AAS7 = 0 (respectively UAS7≤6) assessment is missing, it will be considered as a non-response for the cumulative number of weeks that participants achieve AAS7= 0 response calculation (respectively UAS7≤6).

The negative binomial model accounts for any over dispersion that may result from assuming a Poisson distribution by allowing a different Poisson rate for each patient and assuming that these rates as a set are distributed across participants according to a gamma distribution.

The SAS procedure PROC GENMOD will be used for this analysis with the following code:

```
proc genmod data=...;  
  by impnb;  
  class trt01p antige region/ param = glm;  
  model count = baseline trt01p antige region/ DIST= NEGBIN LINK= LOG  
  offset=offset;  
  lsmeans trt01p / cl exp diff ilink e OM;  
  estimate "LOU064 v.s pbo" trt01p 1 -1;
```

```
ods output Estimates=estimates LSMeans=lsmeans;
run;
```

where baseline = baseline AAS7=0 status (for AAS7 = 0 response only).

The SAS procedure PROC MIANALYZE will be used to combine the results. The risk ratio and the 95% confidence interval for the risk ratio will be generated using an exponential transformation of the model estimates.

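### The tested count of weeks with UAS7≤6 is the only tested efficacy endpoint whose model has no baseline measure of its own outcome: a matter of efficiency and consistency, not of validity.

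*SAP*

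**What the plan says.** Protocol 12.5.1 specifies this count "using a negative binomial regression model with log link, using treatment group, region, and prior exposure to anti-IgE biologics", plus an offset. SAP 2.5.2.2 item 7 repeats those covariates, with the count "modelled using a negative binomial regression model with log link, using treatment group, region, and prior exposure to anti-IgE biologics", so the two documents agree.

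The other tested efficacy endpoints are handled differently:

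- UAS7≤6 at Week 12, UAS7=0 at Week 12 and UAS7≤6 at Week 2 each use a "logistic regression model including treatment group, region, prior exposure to anti-IgE biologics and baseline UAS7 score as covariate" (SAP 2.5.2.2 items 1, 2 and 5).
- DLQI 0/1 adjusts for baseline DLQI (item 6).
- The change scores in UAS7, ISS7 and HSS7 adjust for the matching baseline score and its interaction with week (SAP 2.5.1.2, 2.5.2.2, 2.6.1.2).
- The other count endpoint, weeks with AAS7=0, adjusts for "region, prior exposure to anti-IgE biologics and baseline AAS7 = 0 status" (item 8).

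The negative binomial code in SAP 5.4.2.3 is shared by both counts and contains a baseline term, but the note beneath it reads "where baseline = baseline AAS7=0 status (for AAS7 = 0 response only". The code therefore does not bring baseline UAS7 into the UAS7≤6 count.

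**The concern.** UAS7≤6 is a fixed target. Entry requires "UAS7 score (range 0-42) ≥ 16" (Protocol 5.1), so a controlled week needs a fall of 16 − 6 = 10 points from the lowest entry score and 42 − 6 = 36 from the highest. Starting severity can be expected to affect both when the first controlled week comes and how many follow. Randomization is stratified by region and prior anti-IgE use only (Protocol 6.4.2), so the design does not balance severity.

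Nothing else in the plan fills the gap. The allowance for further covariates is written for the repeated-measures model. Sensitivity analyses for secondary endpoints are marked not applicable (SAP 2.5.2.5). The covariate-adjusted supplementary analysis covers binary endpoints only (SAP 2.5.2.6). Meanwhile SAP 5.4.3 uses baseline UAS7 to impute the scores from which this count is built.

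At stake are some precision and protection from chance imbalance on a confirmatory endpoint. Because testing is strictly hierarchical, failure here would also stop the AAS7=0 count from being tested.

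**Working it through.** **1. The plan's own figure.** No power is stated for this count. The nearest figure is for UAS7≤6 at Week 12 (SAP 3.2): 0.53 versus 0.15, n = 270 and 135, continuity-corrected test, one-sided 0.025, power above 99%.

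- Pooled proportion: (270 × 0.53 + 135 × 0.15)/405 = 0.403
- SE under the null: √(0.403 × 0.597 × (1/135 + 1/270)) = 0.0517
- SE under the alternative: √(0.15 × 0.85/135 + 0.53 × 0.47/270) = 0.0432
- Corrected difference: 0.38 − 0.5 × (1/135 + 1/270) = 0.3744
- z = (0.3744 − 1.96 × 0.0517)/0.0432 ≈ 6.3, so power exceeds 0.9999. The stated figure is reproduced.

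**2. Effect of adding baseline UAS7, by simulation.** From the documents: 300 and 150 participants, 12 weekly indicators, proportions 0.53 and 0.15. Assumed: baseline UAS7 normal (mean 30, SD 8) truncated to 16-42, giving mean 29.6 and SD 6.25; within-person correlation 0.75; correlation ρ between baseline and the underlying weekly score; no dropout, offset or strata. There were 600 trials per row.

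| ρ | Model SE of log rate ratio, without → with | Reduction | Empirical SD, without → with |
|---|---|---|---|
| 0.2 | 0.1290 → 0.1278 | 0.9% | 0.158 → 0.162 |
| 0.3 | 0.1291 → 0.1259 | 2.5% | 0.156 → 0.152 |
| 0.4 | 0.1292 → 0.1232 | 4.6% | 0.157 → 0.153 |
| 0.5 | 0.1295 → 0.1193 | 7.9% | 0.150 → 0.137 |

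Every simulated trial rejected the null, with or without baseline.

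**3. A much weaker effect.** Take 0.40 versus 0.31. The placebo value is close to the Phase 2b Week 12 rate of 31.3% in Protocol 4.2; the 0.40 is hypothetical. Power without → with baseline was 0.54 → 0.57 (ρ 0.2), 0.49 → 0.60 (0.3), 0.49 → 0.64 (0.4) and 0.50 → 0.73 (0.5). With robust standard errors the gain was smaller: 0.70 → 0.70, 0.66 → 0.70, 0.64 → 0.71 and 0.66 → 0.75.

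**4. No effect (0.25 versus 0.25, 1,500 trials).** One-sided rejection was 0.015 without and 0.025 with baseline at ρ 0.3, and 0.009 and 0.024 at ρ 0.5. The planned test is conservative here, not inflated, which explains part of the power gain in step 3.

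**5. Chance imbalance.** One SE of the between-arm baseline difference is 6.25 × √(1/300 + 1/150) = 6.25 × 0.1 = 0.625, about 0.63 points.

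The slope of log count on baseline is not in the documents. Simulating a 10-point Week 12 difference, with baseline carrying forward at 0.3, 0.6 or 1.0 points per point, gave slopes of −0.034, −0.068 and −0.110 per point. A one-SE imbalance then moves the unadjusted rate ratio by:

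- exp(0.034 × 0.625) = 1.02
- exp(0.068 × 0.625) = 1.04
- exp(0.110 × 0.625) = 1.07

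The step 2 simulation agrees. The log rate ratio shifted by 0.193 per SD of imbalance at ρ 0.2 and by 0.690 at ρ 0.5, and one SE is 0.1 SD: exp(0.0193) = 1.02 and exp(0.069) = 1.07. At ρ 0.5 with baseline in the model the shift per SD was 0.187, so exp(0.0187) = 1.02.

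**The case against.** The strongest reply is that nothing is broken. The model is pre-specified, protocol and SAP agree, it adjusts for both stratification factors, and randomization makes the comparison valid without baseline. The choice of a further prognostic covariate is a design preference. At the planned effect it changes no decision: in the simulation with a 10-point difference, the mean Wald z without baseline was at least 5.3 (0.96/0.181), against a critical value of 1.96. The precision gain is also thin and depends on the measure, since the empirical SD did not fall in every scenario; a count bounded at 0-12 is not a good fit to a negative binomial. All of this stands, and it limits the size of the point. It does not explain why this endpoint alone lacks the adjustment.

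Four stronger readings are tempting and are not supported:

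- **Leaving out baseline attenuates the rate ratio.** A log-link rate ratio is essentially collapsible, unlike an odds ratio. In 300,000 simulated negative binomial records with a true log rate ratio of 1.0 and a baseline slope of −0.11, the estimate was 1.003 without baseline and 1.001 with it. Larger estimates after adjustment in the bounded-count simulations reflect model misfit, not a general cost of omission.
- **Adding baseline would make this result comparable with the other UAS7≤6 results.** Those are odds ratios at one visit; this is a rate ratio over 12 weeks (SAP Table 2-12).
- **The plan contradicts Amendment 1.** Its rationale mentions "the use of the same covariates in both primary and secondary endpoints", but an amendment summary is context only, and its listed change to Section 12.5.1 concerns ISS7 and HSS7.
- **The change can be made under the blind.** SAP amendments 2 to 4 are labelled as preceding the primary analysis, whereas amendment 5 (24-Jan-2024) is labelled as preceding the final analysis. Formal testing takes place only at the primary analysis (SAP 2.13). The documents do not say whether that analysis has been run.

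**Conclusion.** The point holds as one of efficiency and consistency. The omission is real, is the same in both documents, is unexplained, and is unique among the tested efficacy endpoints. The prose of SAP 5.4.2.1 also leaves baseline out of the logistic models, but its code and SAP 2.5.2.2 include it, so the uniqueness stands.

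The consequence is modest. In the simulations type I error stayed at or below 0.025, and power at the planned effect is about 100% with or without baseline. The 1-8% lower model standard error rests on an assumed ρ of 0.2 to 0.5. The 2-7% movement from a one-SE imbalance rests on an assumed baseline distribution and assumed slopes. The power gain matters only if the effect is far below plan. A reader should not conclude that the planned test is invalid or underpowered.

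**What to change.** If the primary analysis has not been run:

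- Add continuous baseline UAS7 to the negative binomial model for this endpoint in SAP 2.5.2.2 item 7, SAP 5.4.2.3 and Protocol 12.5.1.
- State under the code that the baseline term is baseline UAS7 for the UAS7≤6 count and baseline AAS7=0 status for the AAS7=0 count.
- Record the change in SAP section 4, which now reports none.

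If the primary analysis has been run, leave the tested model as it is and report the baseline-adjusted model as a labelled supplementary analysis. Changing a tested endpoint's model at that stage would be post hoc.

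The cost is one covariate in an existing model, with no new data. Before the primary analysis it also means wording changes in the protocol and SAP.
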